### 3.4 Primary Safety Endpoints

This is a Phase 4 study using an agent with demonstrated efficacy and safety in all stages of RA. Most relevant to this study, the efficacy and safety of Abatacept in combination with MTX in early RA has already been demonstrated.

## 4 Subject Selection and Withdrawal

### 4.1 Inclusion Criteria

#### 1. Signed Written Informed Consent

- a) Subject is willing to participate in the study and has signed the informed consent.

#### 2. Target Population

- a) Men or women (not nursing or pregnant) over 18 years old who have active RA, defined as symptoms of RA prior to screening and have satisfied the ACR/EULAR 2010 criteria for the classification of RA prior to signing the informed consent.
- b) Subjects must have a DAS28CRP or CDAI assessment at screening and have at least 3 tender and at least 3 swollen joints (excluding distal interphalangeal joints) at screening and at Day 1. Patients must have at least moderate disease activity [CDAI>16); DAS28CRP ( $\geq 4.0$ )].
- c) Subjects must be naive to biologic DMARDs
- d) Subjects must be naive to targeted synthetic DMARDs such as tofacitinib, baricitinib, and investigational therapies for RA.
- e) Subjects receiving oral corticosteroids must be on a stable dose and at the equivalent of 10 mg prednisone daily for at least 4 weeks. Subjects may not receive an IM, IV or IA administration of a corticosteroid within 4 weeks prior to screening visit or initiation of therapy
- f) Patients with prior (including discontinued) therapy with Methotrexate and/or Hydroxychloroquine are permitted as long as they meet other inclusionary criteria.
- g) Subjects must have a DAS28CRP or CDAI at screening and have at least 3 tender and at least 3 swollen joints (excluding distal interphalangeal joints) at screening and at Day 1.

#### Age and Reproductive Status

- a) Men and women, age's  $\geq 18$  years (or age of majority)
- b) Women of childbearing potential (WOCBP) must have a negative serum or urine pregnancy test (minimum sensitivity 25 IU/L or equivalent units of HCG) within 24 hours prior to the start of study drug.
- c) Women must not be breastfeeding and must agree not to breastfeed during the study and for 100 days thereafter
- d) WOCBP must agree to follow instructions for method(s) of contraception for the duration of treatment with study drug plus 5 half-lives of study drug (70 days) plus 30 days (duration of ovulatory cycle) for a total of 100 days post-treatment completion.
- e) Males who are sexually active with WOCBP must agree to follow instructions for

method(s) of contraception for the duration of treatment with study drug, plus 5 half-lives of the study drug (70 days) plus 90 days (duration of sperm turnover) for a total of 160 days post-treatment completion.

f) Azoospermic males and WOCBP who are continuously not heterosexually active are exempt from contraceptive requirements. However they must still undergo pregnancy testing as described in this section. Investigators shall counsel WOCBP and male subjects who are sexually active with WOCBP on the importance of pregnancy prevention and the implications of an unexpected pregnancy.

Investigators shall advise WOCBP and male subjects who are sexually active with WOCBP on the use of highly effective methods of contraception. Highly effective methods of contraception have a failure rate of < 1% when used consistently and correctly.

At a minimum, subjects must agree to use one highly effective method of contraception as listed below.

### **HIGHLY EFFECTIVE METHODS OF CONTRACEPTION**

Highly effective methods of contraception have a failure rate of < 1% when used consistently and correctly. WOCBP and female partners of male subjects, who are WOCBP, are expected to use one of the highly effective methods of contraception listed below. Male subjects must inform their female partners who are WOCBP of the contraceptive requirements of the protocol and are expected to adhere to using contraception with their partner.

- 1) Progestogen only hormonal contraception associated with inhibition of ovulation.
- 2) Hormonal methods of contraception including oral contraceptive pills containing estrogen + progesterone, vaginal ring, injectables, implants and intrauterine devices (IUDs) such as Mirena®.
- 3) Nonhormonal IUDs, such as ParaGard®
- 4) Bilateral Tubal occlusion
- 5) Vasectomized partner with documented azoospermia 90 days after procedure  
Vasectomized partner is a highly effective birth control method provided that partner is the sole sexual partner of the WOCBP trial participant and that the vasectomized partner has received medical assessment of the surgical success.
- 6) Intrauterine hormone-releasing system (IUS)
- 7) Complete abstinence- Complete abstinence is defined as the complete avoidance of heterosexual intercourse
  - a) Complete abstinence is an acceptable form of contraception for all study drugs and must be used throughout the duration of the study treatment (plus 5 half-lives of the investigational drug plus 30 days).
  - b) It is not necessary to use any other method of contraception when complete abstinence is elected.
  - c) Subjects who choose complete abstinence must continue to have pregnancy tests

- d) Acceptable alternate methods of highly effective contraception must be discussed in the event that the subject chooses to forego complete abstinence.
- e) The reliability of sexual abstinence needs to be evaluated in relation to the duration of the clinical trial and the preferred and usual lifestyle of the subject.

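### The abstinence item in the contraception list (item 7a) states only the 100-day period for women, although the list also serves male subjects, whose period is 160 days if sexually active with a woman of childbearing potential

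*Combined protocol and SAP*

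**What the plan says.** Three pieces of section 4.1 (Inclusion Criteria) bear on this.

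**The two periods.** Under Age and Reproductive Status, item (d) requires WOCBP to use contraception during treatment "plus 5 half-lives of study drug (70 days) plus 30 days (duration of ovulatory cycle) for a total of 100 days post-treatment completion". Item (e) uses the same five half-lives for men who are sexually active with WOCBP, but adds a longer second term: "plus 90 days (duration of sperm turnover) for a total of 160 days post-treatment completion".

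**Who uses the method list.** The same subsection says "Investigators shall advise WOCBP and male subjects who are sexually active with WOCBP on the use of highly effective methods of contraception", and then, with no limit by sex, "At a minimum, subjects must agree to use one highly effective method of contraception as listed below". The lead-in to Highly Effective Methods of Contraception says "WOCBP and female partners of male subjects, who are WOCBP, are expected to use one of the highly effective methods of contraception listed below". It also tells male subjects to pass the protocol's requirements on to their partners and to adhere to contraception with them.

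**The abstinence item.** Seven methods are listed. Item 7 is complete abstinence, and 7a says it "must be used throughout the duration of the study treatment (plus 5 half-lives of the investigational drug plus 30 days"). Item 7b adds that nothing further is needed once abstinence is elected. Item 7c says "Subjects who choose complete abstinence must continue to have pregnancy tests". Item 7d requires alternatives to be discussed if the subject gives abstinence up, but attaches no time period to that.

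**The concern.** The 30 days in item 7a is the term that item (d) justifies by the ovulatory cycle. Item (e) uses 90 days for men and gives sperm turnover as the reason. A method list that serves both groups therefore carries the women's end date alone at the one point where it states an end date at all.

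Item 7 reads as a complete instruction: choose abstinence, use nothing else, continue to a stated date. Site staff counselling a male subject or his partner from that item could give day 100. If the man then resumed intercourse without contraception, he would be inside the 160-day period and item 7a would not have told him so. The protocol treats pregnancy in a male subject's partner as a matter for safety reporting (section 7.1, Pregnancy), so the point belongs to partner safety. It does not touch the trial's inference.

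**Working it through.** **Inputs, all from section 4.1**

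- Five half-lives of study drug: 70 days, items (d) and (e). The implied half-life is 70 / 5 = 14 days.
- Added term for WOCBP: 30 days, item (d).
- Added term for men: 90 days, item (e).
- Added term for abstinence: 30 days, item 7a.

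**The protocol's own totals**

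- WOCBP: 70 + 30 = 100 days, as stated in (d).
- Men: 70 + 90 = 160 days, as stated in (e).

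**Item 7a on the same basis**

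- 70 + 30 = 100 days for anyone who elects abstinence.
- Gap to the male period: 160 - 100 = 60 days. That is 60 / 7 = 8.6 weeks, or 60 / 160 = 37.5% of the period in (e).

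**Is item 7 alone in this?** Of the seven methods, only item 7 states a post-treatment duration. The 90 days in item 5 concerns confirmation of azoospermia after vasectomy and is not a post-treatment period. The other 7 - 1 = 6 methods state none, so they take their period from (d) or (e) and no mismatch arises.

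**When the window falls.** Section 1.5 places infusions at weeks 0, 2 and 4 and then every 4 weeks to a total of seven: weeks 0, 2, 4, 8, 12, 16 and 20. The last is on day 140. Assuming treatment completion means the last infusion, the window runs from day 140 + 100 = 240 (week 34.3) to day 140 + 160 = 300 (week 42.9). Assuming instead that it means week 24 (day 168), the window is day 268 to day 328 (weeks 38.3 to 46.9). Either way it lies inside the 52-week study, so for subjects still in follow-up the question can come up at the site.

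**How many subjects.** The documents do not allow a count. If the female-to-male ratio of 2 to 3 in section 1.1 held among the 25 subjects, there would be about 25 / 4 = 6 to 25 / 3 = 8 men. Those affected would also need a WOCBP partner, would have to choose complete abstinence, and would have to end it between day 100 and day 160.

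**The case against.** The strongest reply is that the two rules do not collide. Item (e) covers only men who are sexually active with WOCBP, and item 7 defines abstinence as having no heterosexual intercourse. A man who abstains is arguably outside (e) for as long as he does so. If he resumes with a WOCBP before day 160, (e) applies again and requires contraception to day 160. This stands. A reader might infer that 7a lets men stop at day 100, or that the protocol contradicts itself for a man who remains abstinent. The documents support neither reading: nothing in 7a displaces (e).

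A second reply is that item 7 was written for female subjects. Its 30-day term comes from (d), and the pregnancy tests in 7c fit only women. This is probably how the text arose. But 7a is not limited to women, the closing sentence of Age and Reproductive Status sends all subjects to the list, and the lead-in names the WOCBP partners of male subjects. Item (f) does not clearly exempt abstinent men either.

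A third reply is that resumption is already covered, by 7d and by the duty to advise sexually active men. This holds only in part. Item 7d gives no duration, and it concerns someone who gives abstinence up. A man who has completed the period in 7a could reasonably think he had met the requirement.

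Finally, the practical consequence is small and cannot be demonstrated. That is accepted.

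**Conclusion.** The point holds as a minor inconsistency in safety text. Item 7a gives one end date, 100 days, in a list that also serves men and their partners, and does not mention that the period for men sexually active with WOCBP runs 60 days longer. What is missing is a warning to a male subject who elects abstinence and takes 7a's end date as his own.

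This rests on reading the list as serving both sexes, which its lead-in and the closing sentence of Age and Reproductive Status support, and on the protocol's own 70 days for five half-lives. It does not require abstinent men to fall under (e), and it does not claim that 7a authorises a shorter period. The arithmetic is certain. The number affected is unknown, probably very small and possibly zero. Endpoints, analysis and sample size are unaffected.

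**What to change.** In item 7a, replace the parenthesis with: *plus the post-treatment period in 4.1, Age and Reproductive Status: 100 days for WOCBP (d); 160 days for male subjects with WOCBP partners (e), with another highly effective method required if abstinence ends before then.* Name the subsection in the reference, because Target Population in section 4.1 also has items lettered (d) and (e).

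Align any consent text that repeats the abstinence period. The consent form is not among the pages available for this review, so whether it does so could not be checked.

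The cost is one wording edit and any matching consent change. The edit uses the protocol's own figures.

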## **UNACCEPTABLE METHODS OF CONTRACEPTION**

- 1) Periodic abstinence (calendar, symptothermal, post-ovulation methods)
- 2) Withdrawal (coitus interruptus)
- 3) Spermicide only
- 4) Lactation amenorrhea method (LAM)

### **4.2      *Exclusion Criteria***

#### **1. Target Disease Exceptions**

- a) Subjects with autoimmune disease other than RA [e.g., psoriasis, systemic lupus erythematosus (SLE), vasculitis, seronegative spondyloarthritis, Inflammatory Bowel Disease, Sjogren's syndrome] or currently active fibromyalgia.
- b) Prior history of or current inflammatory joint disease other than RA (such as psoriatic arthritis, gout, reactive arthritis, Lyme disease).

#### **2. Medical History and Concurrent Diseases**

- a) Subjects at risk for tuberculosis (TB) defined as follows:  
Current clinical, radiographic or laboratory evidence of active TB. Chest x-rays (posterior anterior and lateral) obtained within the 3 months prior to obtaining written informed consent will be permitted but the images must be available and reviewed by the investigator. TB testing (IFN-gamma release assay or PPD) performed in the past month prior to Screening will be accepted; however, a copy of the report must be placed in the subject binder.

- b) A history of active TB
- c) Subjects with a positive TB screening test indicative of latent TB will not be eligible for the study unless they:

- 1) Have no evidence of current TB based on chest x-ray performed  
And they are actively being treated for TB or the site has  
documentation of successful prior treatment of latent TB. Treatment  
regimens should be dictated by local guidelines as long as the  
treatment dose and duration meet or exceed local health authority  
guidelines.

- b) Subjects with recent acute infection defined as:
  - 1) Any acute infection within 60 days prior to randomization that required hospitalization or treatment with parenteral antibiotics.

- 2) Any acute infection within 30 days prior to randomization that required oral antimicrobial or antiviral therapy.
- c) Subjects with history of chronic or recurrent bacterial infection (such as chronic pyelonephritis, osteomyelitis, and bronchiectasis etc.).
- d) Subjects with any history of infection of a joint prosthesis or artificial joint.
- e) Subjects who have a history of systemic fungal infections (such as histoplasmosis, blastomycosis, or coccidiomycosis).
- f) Subjects with history of recurrent herpes zoster (more than 1 episode) or disseminated (more than 1 dermatome) herpes zoster or disseminated herpes simplex, or ophthalmic zoster will be excluded. Symptoms of herpes zoster or herpes simplex must have resolved more than 60 days prior to screening.
- g) Subjects with history of Human Immunodeficiency Virus (HIV) infection or who tested positive for HIV
- h) Subjects with history of primary immunodeficiency
- i) Subjects who have a present malignancy or previous malignancy within the last 5 years prior to screening (except documented history of cured non-metastatic squamous or basal cell skin carcinoma or cervical carcinoma in situ). Subjects who had a screening procedure that is suspicious for malignancy, and in whom the possibility of malignancy cannot be reasonably excluded following additional clinical, laboratory or other diagnostic evaluations.
- j) Current clinical findings or a history of a demyelinating disorder
- k) New York Heart Association (NYHA) Class III or IV heart failure
- l) Any previous or current medical conditions that are warnings against the use of TNF inhibitor agents.
- m) Current clinical findings of severe, progressive, or uncontrolled renal, hepatic, hematological, gastrointestinal, pulmonary, psychiatric, cardiac, endocrine, neurological, or cerebral disease including severe and uncontrolled infections, such as sepsis and opportunistic infections. Concomitant medical conditions that, in the opinion of the investigator, might place the subject at unacceptable risk for participation in this study.
- n) Subjects who have received any live vaccines within 3 months of the study drug administration or are scheduled to receive live vaccines during the study. Study subjects should not be administered a live virus vaccine for a minimum of 3 months following the last dose of study medication. Subjects who are in close contact with others who have received a live vaccine may be enrolled at the investigator's discretion.
- o) Subjects who have undergone a major surgical procedure within the 60 days prior to randomization.

p) Subjects for whom 5 or more joints cannot be assessed for tenderness or swelling (i.e. due to surgery, fusion, amputation, etc.).

3. Subjects who are prisoners, or compulsory detained.

### **4.3     *Subject Recruitment and Screening***

Eligibility will be based on specified inclusion and exclusion criteria, medical history, disease activity and safety assessments. Day 1 must occur within 28 days of signing the informed consent. Subjects that experience an acute infection or initiate treatment for latent TB may extend the screening period to 42 days.

Eligible subjects will have had symptoms and diagnosis of RA prior to signing the informed consent. Symptoms of RA are defined as pain, stiffness or swelling in joints which are typically inflamed in RA. Subjects must also have fulfilled criteria for rheumatoid arthritis by ACR/EULAR 2010 classification prior to signing informed consent.

Subjects treated with MTX must remain on a stable dose of oral methotrexate for at least 4 weeks prior to Day 1. The stable dose of oral MTX should be the maximum tolerated dose (minimum of 15 mg and maximum of 25 mg per week). A dose of methotrexate 7.5-12.5mg/week is permitted if intolerance to 15 mg or higher doses has been recorded in the source documents and the dose of oral methotrexate is stable for 4 weeks prior to randomization.

To minimize potential methotrexate toxicity, all subjects must receive folic acid, folinic acid, or leucovorin according to the manufacturer recommendations, methotrexate label instructions, and the local medical standard of care guidelines. Subjects receiving oral corticosteroids must be on a stable dose and at the equivalent of 10 mg prednisone daily for at least 4 weeks prior to randomization. Subjects may not have received an IM, IV or IA administration of a corticosteroid within 4 weeks prior to randomization.

### **4.4     *Early Withdrawal of Subjects***

#### **4.4.1   *When and How to Withdraw Subjects***

All subjects who have received at least one dose of study drug and exit the study early will complete an early termination (ET) visit at the time of study discontinuation. Subjects will continue standard of care appointments with their primary rheumatologist after ET visit.

#### **4.4.2   *Data Collection and Follow-up for Withdrawn Subjects***

All reasonable efforts must be made to locate subjects to determine and report their ongoing status. This includes follow-up with persons authorized by the subject. Lost

to follow-up is defined by the inability to reach the subject after a minimum of 3 documented phone calls, faxes or emails (not performed on the same day), as well as a lack of response by the subject to 1 registered mail letter. All attempts should be documented in the subject's medical records. If it is determined that the subject has died, the site will use permissible local methods to obtain the date and cause of death and as much other information as can be obtained, including post-mortem reports. Data to be collected at subsequent visits will be considered missing.

#### 4.2.1 End of Study

At the end of the study period, Bristol-Myers Squibb Company will not continue to supply study drug to subjects/investigators unless the Sponsor-Investigator chooses to extend their study. The investigator is responsible to ensure that the subject receives appropriate standard of care or other appropriate treatment in the independent medical judgement of the Investigator to treat the condition under study.

### 5 Study Drug

#### 5.1 *Description and Treatment Regimen*

Abatacept for adult patients with RA, ABATACEPT will be administered as an intravenous infusion. Abatacept will be used concomitantly with DMARDs other than TNF antagonists or JAK inhibitors. Intravenous Dosing Regimen Abatacept lyophilized powder should be reconstituted and administered after dilution [see Dosage and Administration below] as a 30-minute intravenous infusion utilizing the weight range-based dosing specified. Following the initial intravenous administration, an intravenous infusion should be given at 2 and 4 weeks after the first infusion and every 4 weeks thereafter.

Dose of ABATACEPT for Intravenous Infusion in Adult RA Patients  
Body Weight of Patient Dose Number of Vials

Each vial provides 250 mg of Abatacept for administration.

1.     Less than 60 kg:       500 mg 2 vials
2.     60 to 100 kg:       750 mg 3 vials
3.     More than 100 kg    1000 mg 4 vials

#### Dose Modifications in the Absence of Adverse Events

Subjects should complete their scheduled infusions as described above.

#### Dose Modifications Due to Adverse Events

If abnormal laboratory test results or clinical adverse events indicate toxicity that, in the judgment of the investigator, could place the subject at risk, study drug administration should be interrupted. Subjects may receive further study medication treatment only if full resolution of the adverse event or abnormal laboratory finding is documented. **Under no circumstances should the dose of study drug be altered due to an adverse event.**

## **5.2     *Method for Assigning Subjects to Treatment Groups***

N/A.

## **5.3     *Preparation and Administration of Study Drug***

Abatacept for reconstitution and dilution prior to intravenous administration. Following reconstitution of the lyophilized powder with 10 mL of Sterile Water for Injection, USP, the solution of Abatacept is clear, colorless to pale yellow, with a pH range of 7.2 to 7.8. Each single-use vial of Abatacept for Injection provides 250 mg Abatacept, maltose (500 mg), monobasic sodium phosphate (17.2 mg), and sodium chloride (14.6 mg) for administration.

Reconstitute using only the silicone-free disposable syringe provided with each vial and an 18- to 21-gauge needle. If the Abatacept powder is accidentally reconstituted using a siliconized syringe, the solution may develop a few translucent particles. Discard any solutions prepared using siliconized syringes. Administer the entire, fully diluted Abatacept solution over a period of 30 minutes with an infusion set and a sterile, nonpyrogenic, low-protein-binding filter (pore size of 0.2  $\mu$ m to 1.2  $\mu$ m).

The Dartmouth-Hitchcock Medical Center Investigational Pharmacy will ensure that the study drug is stored in accordance with the environmental conditions (temperature, light, and humidity). If concerns regarding the quality or appearance of the study drug arise, the study drug should not be dispensed. Investigational product documentation will be maintained that includes all processes required to ensure drug is accurately administered. This includes documentation of drug storage, administration and, as applicable, storage temperatures, reconstitution, and use of required processes (eg, required diluents, administration sets).

